An Exploration of the Impact of Emicizumab on the Lives of People with Haemophilia and Inhibitors and their Families

Principal investigators: [name]

Co-Investigators: [name], [name]

Study Sponsor: Haemnet (Registered Charity No 1152241)

Study Coordinator: [name], Haemnet

Version date: 4 November 2019

Version number: Version 4

CONFIDENTIAL

Information and data included in this document contain privileged or confidential information, which is the property of the sponsor. No person is authorised to make it public without written permission of the sponsor. These restrictions on disclosure will apply equally to all future information supplied to you, which is indicated as privileged or confidential. This material may be disclosed to and used by your staff and associates as may be necessary to conduct the clinical study.

List of Abbreviations

| Abbreviation | Definition |
|--------------|--|
| CCC | Comprehensive Care Centre |
| EAMS | Early Access to Medicines Scheme |
| Emi | Emicizumab |
| Haemo-QOL | Haemophilia Quality of Life scale |
| Hep-Test-Q | Haemophilia and Exercise Project Test Questionnaire |
| HJHS | Haemophilia Joint Health Score |
| HRQoL | Health-Related Quality of Life |
| HTC | Haemophilia Treatment Centre |
| PWH | People with Haemophilia |
| QoL | Quality of Life |
| SO-FIT | Study Of physical Function In adolescenTs with haemophilia |

Study Synopsis

| | |
|---------------------------------|--|
| Title | Emi and Me: an exploration of the impact of emicizumab on the lives of people with haemophilia and inhibitors and their families |
| Short Title | Emi and Me |
| Study aim | This study aims to examine the real-life experience and impact of using emicizumab in a cohort of patients with haemophilia and inhibitors, who are being prescribed emicizumab in routine clinical practice as well as those who have been in the clinical trials. We also intend to capture the impact of emicizumab use on the lives of close family members (parents/carers/children/siblings). |
| Primary Objective | To capture the real-life experience of using emicizumab for haemophilia inhibitor therapy for the patient with haemophilia and his close family members |
| Secondary Objectives | To describe difference patient satisfaction with injections (numbers of injections, how to remember treatment dates, and so on). To understand user's expectations of emicizumab and how they see future haemophilia care (less frequent injections, impact on home storage, number of bleeds, reduced hospitalisations and so on). To describe the as yet 'unseen' impact on the extended family – and to seek their views of innovative therapy for haemophilia. |
| Design | Non-interventional qualitative study |
| Number of Centres | N/A (recruitment via social media) |
| Duration | 6 months data collection 12 months total study duration |
| Number of Subjects | 25 'dyad' pairs |
| Inclusion Criteria | Study participants will be people with inhibitors using emicizumab (prescribed by treating clinicians) in usual clinical care. Family members of participants will also be included. |
| Exclusion Criteria | Participants will be excluded from the study if they do not have an inhibitor, are not being treated with emicizumab, do not speak English (for the interviews) or do not consent. |
| Statistical Analysis | This is a qualitative study using established qualitative research methodologies (grounded theory). Statistical evaluation is not appropriate |
| Operational procedures | |
| Ethical approval | NHS ethical approval will be sought from HRA |
| Data analysis | To be conducted by Haemnet |
| Write up and publication | Lead researcher and research team |

Emi and Me

An Exploration of the Impact of Emicizumab on the Lives of People with Haemophilia and Inhibitors and their Families

Index

| | | |
|---|--|------------------------------|
| 1 | Background | 5 |
| 1.1 | Disease Introduction | 5 |
| 1.2 | Rationale for the study..... | 6 |
| 2 | Aim and Objectives | 6 |
| 2.1 | Aim | 6 |
| 2.2 | Primary Objective..... | 6 |
| 2.3 | Secondary Objectives | 7 |
| 3 | Study design | 7 |
| 3.1 | General Design | 7 |
| 3.2 | Primary Endpoints..... | 7 |
| 3.3 | Secondary endpoints..... | 7 |
| 3.4 | Statistical analysis and sample size calculation..... | 8 |
| 4 | Study Group | 8 |
| 4.1 | Inclusion Criteria..... | 8 |
| 4.2 | Exclusion Criteria | 9 |
| 5 | Recruitment, Screening and Study Procedures | 9 |
| 5.1 | Study visits 1 (inclusion) | 9 |
| 5.2 | Study duration..... | 10 |
| 5.3 | Safety reporting..... | 10 |
| 6 | Data analysis plan | 10 |
| 6.1 | Data analysis..... | 10 |
| 7 | Ethics..... | 11 |
| 7.1 | Informed consent..... | 11 |

1.1 Disease Introduction

Haemophilia A is a rare congenital disorder caused by an inherited genetic defect of the X chromosome that results in a deficiency in factor VIII production. Factor VIII plays a pivotal role in the coagulation cascade, bringing together the clotting factors IXa and X, a critical step in the formation of a blood clot to help stop bleeding. Haemophilia A results in impaired clot formation and can lead to uncontrolled and often spontaneous bleeding. It affects approximately one in every 5,000 males [Srivastava et al, 2013]. Different types of severity are recognised:

- “severe” (factor activity is less than 1%)
- “moderate” (factor activity is 1-5%)
- “mild” (factor activity is 6-25%).

In its severe form, haemophilia results in recurrent joint and muscle bleeds that predispose to arthropathy, muscle contracture and disability. Treatment of affected individuals in the UK is with FVIII prophylaxis, which decreases spontaneous bleeding events and resultant joint damage [Richards et al, 2010]. Prophylaxis requires frequent intravenous infusions, which can be as often as daily but are usually 2-3 times per week.

A serious complication of treatment is the development of inhibitors to infused factor VIII replacement therapies. Inhibitors are antibodies developed by the body's immune system that bind to and block the efficacy of replacement factor VIII, making it difficult, if not impossible to obtain a level of factor VIII sufficient to control bleeding. Up to 40% of patients receiving replacement factor develop inhibitors [Iorio et al, 2017].

Of these patients, who are predominantly children, between 50 and 86% can be tolerised through extended periods of very high treatment [Holstein et al, 2016]. Unfortunately, for a small number of these children, this treatment fails leaving a cohort of young children/adolescents who join a group of adults who never had access to this treatment [Khair et al, 2018]. For this ever-growing cohort of individuals treatment is with bypassing agent therapy either when bleed occur (on-demand or episodic therapy) or as prophylaxis [Dekoven et al, 2013].

Treatment of inhibitors is burdensome for the patient and his family [Lindvall et al, 2014; DeKoven et al, 2014] as it requires repeated intravenous infusions. Furthermore, treatment does not always alleviate bleeding, which can result in haemophiliac arthropathy, reduced mobility and pain and frequent episodes of hospital delivered care [Berntorp et al, 2011].

Emicizumab is a bispecific factor IXa- and factor X-directed humanised monoclonal antibody that has been co-developed by Chugai, Roche and Genentech. It has been designed to mimic the activity of factor VIII bringing together factor IXa and factor X, proteins that are required to activate the natural coagulation cascade and restore the blood clotting process for haemophilia A patients. Emicizumab is a prophylactic (preventative) treatment that can be administered by an injection of a ready-to-use solution under the skin (subcutaneously) once weekly or potentially once monthly following initial weekly ‘loading’ doses [Shima et al, 2016]. In a pivotal phase III study, which compared emicizumab with on-demand (no prophylaxis) and prophylaxis use of bypassing agents (BPAs) in adults and adolescents with haemophilia A with inhibitors, the primary endpoint showed a clinically meaningful and statistically significant reduction in treated bleeds of 87% (risk rate [RR]=0.13, p<0.0001) with emicizumab prophylaxis [Oldenburg et al, 2017]. Furthermore, over a median observation time of 31 weeks, substantially more patients experienced zero bleeds with emicizumab prophylaxis.

Consequently, patient expectation of emicizumab is significant. On haemophilia-specific social media websites, many patients have expressed optimism for a treatment likely to result in reduced treatment burden and fewer bleeds, with a consequent impact on mobility and pain. Treatment burden also includes the time commitment required for treatment, which is reported to impact on treatment adherence [Thornburg, 2018]. The frequency of infusion of current therapy is often cited as influencing adherence to treatment; decreased frequency of infusions and sub-cutaneous administration may encourage adherence and better treatment outcomes [Hacker et al, 2001].

1.2 Rationale for the study

Emicizumab offers patients protection from bleeding with fewer injections, this should reduce treatment burden. While patient expectation is high (as evidenced by the conversations on UK haemophilia social media sites) there are risks that patients may forget to treat and thus experience bleeds. During clinical trials participants have been monitored closely and, through questionnaire completion, have described improvement in quality of life [Mancuso et al, 2018, Oldenburg et al 2019].

What is also apparent to clinical teams is the dramatic change to life experience of not just the patient but his family – the ability to travel, to plan attending events knowing that bleeds will not occur, even potentially to have another child because of the reduction in treatment burden, particularly the time needed for treatment and rehabilitation.

This therapy represents a substantial shift in the entire life experience of living with and managing haemophilia with inhibitors. As such, there is a need to look beyond the quantitative data collected in clinical trials and to assess the real impact of therapy on the everyday lives of patients and their families, gathered using qualitative research techniques.

Emicizumab has been available in the UK in clinical trials and as part of an Early Access to Medicines Scheme (EAMS) for non-trial eligible patients since spring 2018. It was recently licensed in the UK and is now available for routine clinical care for any person with haemophilia A and an inhibitor.

We hypothesise that patients and their carers/families will be excited about this new treatment option and that for most, if not all, the promise of improved care and quality of life will be a reality.

2 Aim and Objectives

2.1 Aim

This study aims to examine the real-life experience and impact of using emicizumab in a cohort of patients with haemophilia and inhibitors, who are being prescribed emicizumab in routine clinical care or as part of the EAMS process as well as those who have been in the clinical trials. We also intend to capture the impact of emicizumab use on the lives of close family members (parents/carers/children/siblings). Each participant and his family members will be deemed a study 'dyad'.

2.2 Primary Objective

To capture the real-life experience of using emicizumab for haemophilia inhibitor therapy for the patient with haemophilia and his close family members.

2.3 Secondary Objectives

- To describe difference patient satisfaction with injections (numbers of injections, how to remember treatment dates etc).
- To understand user's expectations of emicizumab and how they see future haemophilia care (less frequent injections, impact on home storage, number of bleeds, reduced hospitalisations etc).
- To describe the as yet 'unseen' impact on the extended family – and to seek their views of innovative therapy for haemophilia.

3 Study design

3.1 General Design

This is a prospective, observational cohort qualitative research study to be conducted among patients using emicizumab in routine clinical practice.

The study is designed to allow English-speaking patients and their families to tell their own life stories through narrative accounts. The narratives represent a true sharing of experiences valued by the tellers, listeners and gatherers [Hardy et al, 2009], and therefore offer insight into how these patients and families cope with haemophilia.

Most experienced practitioners familiar with haemophilia have preconceived ideas and theories that may potentially bias data capture. Grounded theory is a research methodology that allows identification and description of the broad spectrum of life with haemophilia from the perspectives of the patient and their families. This methodology enables rich data capture across a large age range and allows for deep consideration of data, allowing research questions to be re-shaped as evolving themes and new concepts emerge.

The study will form part of a PhD by published works undertaken by the PI and supervised by [name].

3.2 Primary Endpoints

To gather a deep and thorough understanding about how switching from factor based products to emicizumab for routine treatment in "real-world" settings meets the needs and changes the perspectives of the patient with haemophilia and his immediate family members.

3.3 Secondary endpoints

- To gather a deeper understanding about how emicizumab is used in real life, how patients remember to treat, and what impact this has had on their ability to engage fully in daily activities.
- To describe patients' views about treatment patterns; given days vs. tailored individualised treatment (once weekly to once monthly injections)
- To understand differences and experiences between participant sub-groups (children/siblings, carers, adult and child patients).
- To develop a greater understanding of where emicizumab fits in the future treatment landscape, which might include use in patients with haemophilia without inhibitors.

3.4 Statistical analysis and sample size calculation

This is a qualitative study using established qualitative research methodologies. Statistical evaluation is not appropriate.

We will start with an interview guide developed by the lead researcher and a patient co-researcher, and tested on three pilot participants (one child, one teenager, one adult).

All interviews will be recorded digitally so that the researcher can pay full attention to the subject, without the need to write down verbatim comments [Balen et al, 2000]. Following each interview, the researcher will also make notes of any thoughts, reflections or observations that arose during the interview.

After each of the interviews, the sound files will be transcribed verbatim; the lead investigators will then analyse the transcripts using a grounded theory approach. Direct quotes are analysed into topics, and topics are coded into themes to identify recurring themes seen as important aspects of life with haemophilia. Each interview is coded as it occurs, following analysis the interview guide is then amended so that emerging themes may be further investigated in later interviews [Charmaz 2006].

This continues until no new data are described (data saturation). This is recognised as being a very effective way to gain deep insightful and rich data from study participants [Bryant and Charmaz, 2010; Charmaz, 2013; Charmaz, 1990, Sim et al, 2018]. The study team have used this methodology in previous haemophilia research studies [Khair et al, 2013; Khair et al 2019 (HOPE study, in press)].

Inferential testing will be used to describe how outcomes differ between groups (e.g. patients vs. parents). Correlation between groups may be achievable with explanatory factors (e.g. age, treatment regimen, bleeds, joint health etc.)

4 Study Group

The study population will comprise people with haemophilia A, of any age or severity, in the UK who have an inhibitor, and their family members. According to the UKHCD0 annual report for April 2016 to March 2017, there are 217 people with an inhibitor listed on the National Haemophilia Database (UKHCD0, 2017).

We estimate that in the UK, around 20 patients have been treated with emicizumab in clinical trials (principally in the major London centres). Around 40 people received therapy with emicizumab as part of the Early Access to Medicines Scheme (EAMS) for non-clinical trial eligible patients. Another small cohort of people have received emicizumab since it was licensed in the UK in May 2018.

From this sub-population of <100 people, we would hope to recruit around 25 to the study, together with at least one family member.

Prescribed doses and frequency of treatment will be decided and prescribed by the patient's clinical team. No patient will switch to emicizumab to gain entry to this study.

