6.1 Data analysis

This study will be analysed using grounded theory. Grounded theory involves gathering rich data, using a variety of methods, including interviews, ethnography and textual analysis identifying themes, coding and analysing these finally developing theories about the data that has emerged [Charmaz, 2006]. Grounded theory has been used extensively in research with children and families [Neill, 2007].

Taped Interviews:

- The interviews will be transcribed and anonymised during the transcription process.
- Once the interviews are transcribed, the text will be read and re-read whilst listening to the recordings to ensure correct transcription. Following this review process and analysis the tapes will be destroyed and the transcripts will become the source data
- The interviews will be coded into themes by the whole research team, the themes will then be analysed further using a transformational framework, identifying overarching themes or concepts, summarising and synthesising the data and using descriptive analysis to represent the findings/dyads views [Spencer et al, 2003].
- A table of the themes will be produced
- These themes will characterise recurring ideas and thoughts from the participants and will form the basis for further analysis and publications.
- Individual quotes may be used – these will be anonymised, this will be in the information sheet(s) and consent.

Field notes:

- Immediately after the interview, the researcher will record any thoughts, reflections or observations made during the interview. In particular any thoughts/ideas about emerging themes will be recorded.
- These notes will be analysed as part of the framework analysis [Ritchie et al, 2003].

7 Ethics

There is minimal risk to participants or researchers from this study. Participants will be invited to one interview to discuss their hopes, fears, expectations and the realities of the new treatment.

In the event that any patient or family member becomes distressed by this they will be referred (with consent) to the psychology services affiliated with the haemophilia centres from which they have been recruited.

National guidance on interviewing children [MRC, 2004; RCPCH, 2000] will be followed.

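### Section 3.4 rules out statistical evaluation and then commits to inferential testing between groups; the data analysis section (6.1) names no test

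*Protocol*

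**What the plan says.** Section 3.4 of the protocol, on statistical analysis and sample size, describes the study as qualitative and states: "Statistical evaluation is not appropriate". The statistical analysis row of the synopsis carries the same statement.

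The last paragraph of 3.4 says: "Inferential testing will be used to describe how outcomes differ between groups (e.g. patients vs. parents". It goes on: "Correlation between groups may be achievable with explanatory factors (e.g. age, treatment regimen, bleeds, joint health etc".

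Section 6.1 begins: "This study will be analysed using grounded theory". It then describes coding into themes, a table of themes, framework analysis of the field notes, and "using descriptive analysis to represent the findings/dyads views". It mentions neither a test nor a correlation.

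The surrounding sections are in keeping with a purely qualitative study. Section 1.2 argues that "there is a need to look beyond the quantitative data collected in clinical trials", and section 3.1 calls the study qualitative research. Section 3.3 lists understanding differences between participant sub-groups as a secondary endpoint, without naming a quantitative outcome.

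**The concern.** One section both excludes statistical evaluation and promises it. An analyst who follows the last paragraph of 3.4 would report p-values for group differences. An analyst who follows the opening of 3.4, the synopsis and 6.1 would report none. Each could claim to have kept to the protocol, so it gives no protection against tests being reported selectively.

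The part of the study most likely to be touched is the sub-group endpoint in 3.3. That link is inferred, because 3.4 does not cite the endpoint. The primary objective, to capture lived experience, does not depend on any test.

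**Working it through.** The protocol gives no significance level, power, effect size or variance, and the target of 25 dyads is not presented as a calculated figure. There is no sample size to reproduce, so the check is a comparison of texts plus one count.

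**Step 1: the statements side by side.**

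| Place | Position on statistical testing |
|---|---|
| Synopsis, statistical analysis row | Ruled out |
| 3.4, opening | Ruled out (same statement) |
| 3.4, last paragraph, first sentence | Committed to, without condition |
| 3.4, last paragraph, second sentence | Correlation raised as a possibility only |
| 6.1 | Silent; qualitative and descriptive methods only |

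The conflict lies between the second and third rows. The exclusion carries no qualifier, such as a restriction to the primary analysis or to sample size. The commitment is definite. The correlation sentence is conditional, and the finding does not rest on it.

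**Step 2: does another section settle it?** Section 6.1 is where a test would be expected, and none is there. The endpoint in 3.3 can be met by qualitative comparison. Nothing else in the protocol reconciles the two statements.

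**Step 3: would tests suit the design as described?** There are two difficulties, and they concern different comparisons.

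- *Between families, for example adult versus child patients.* Section 3.4 says that "following analysis the interview guide is then amended so that emerging themes may be further investigated in later interviews", and section 3.1 describes grounded theory as "allowing research questions to be re-shaped as evolving themes and new concepts emerge". Early and late participants are therefore not asked the same things. Whether a theme is mentioned depends partly on when the interview took place, so counts of mentions are not collected uniformly across unpaired groups.
- *Within families, for example patients versus relatives.* Section 2.1 defines each patient and his family members as one dyad, so their answers are not independent.

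**Step 4: the count.** Inputs: 25 dyads (synopsis); around 25 patients, each with at least one family member (section 4).

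- People: 25 + (25 × 1) = at least 50.
- Independent families: 25.

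A patient versus relative comparison rests on about 25 independent families, not on 50 or more independent people. A comparison with parents specifically may rest on fewer, because section 4.1 names parents only for children under 16. The protocol does not say how many such families are expected.

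**The case against.** The contradiction in 3.4 is hard to dispute. The best opposing case is aimed at what surrounds it.

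- **The changing guide does not clearly harm the comparison the protocol uses as its example.** Section 5.2 says each dyad is interviewed once. If patient and parent are seen together, they meet the same version of the guide. This stands: the guide problem applies to unpaired groups, and pairing is the issue for patients versus parents.
- **Pairing is not a loss in itself.** A paired comparison can be more precise than an unpaired one. This also stands: the error would lie in ignoring the pairing. The figure of 25 is, moreover, a recruitment hope, and interviewing continues until saturation.
- **Analysis detail belongs in a statistical analysis plan.** That answers a complaint about missing detail, but not this one. A plan that specified tests would contradict the opening of 3.4 and the synopsis; a plan without tests would contradict the last paragraph of 3.4.
- **The supporting sections are weaker evidence.** Section 1.2 gives motivation and forbids nothing. Section 6.1 is silent on tests and leaves room for further analysis of the themes. The synopsis and 3.4 repeat one statement. All fair, but the clash within 3.4 is enough alone.
- **Quantitative measures may exist.** The panel in 5.1 is not visible in the copy reviewed, the abbreviation list includes HJHS, Haemo-QOL and Hep-Test-Q, and 3.4 mentions bleeds and joint health. Deleting the paragraph could discard an intended analysis. This point bears on the choice of remedy. It does not remove the contradiction.

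**Conclusion.** The concern holds. The protocol excludes statistical evaluation in two places and commits to inferential testing in one, and no other section resolves the conflict. No numerical effect is claimed. The only figure, about 25 families behind at least 50 people, assumes the recruitment target is met with one or more relatives per patient.

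The conclusion rests on the wording alone and does not depend on whether fixed quantitative measures are collected. It should be fixed, because a reader cannot tell which analysis of group differences was planned, but it leaves the primary qualitative objective intact.

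**What to change.** **Preferred.** Replace the last paragraph of 3.4 with text such as: *Differences between patients, family members and sub-groups will be described qualitatively. No hypothesis tests or correlations will be performed.* This brings 3.4 into line with the synopsis and 6.1. It costs one paragraph of rewording and the loss of the group tests; interviews and recruitment are unchanged.

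**Alternative, only if fixed quantitative measures are collected and the sponsor wants tests.** Withdraw the exclusion of statistical evaluation from both the synopsis and the opening of 3.4. Then state in 6.1 which measures are analysed, which groups are compared, and how the analysis accounts for patients and relatives belonging to the same family. This costs more, as it needs an added analysis section as well as both withdrawals.

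The sponsor can choose between the two by checking what the 5.1 panel lists.
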